7.2 Participant Withdrawal from the Study

- A participant may withdraw from the study at any time at his/her own request, or may be withdrawn at any time at the discretion of the investigator for safety, behavioural, compliance, or administrative reasons. This is expected to be uncommon.
- A participant who considers withdrawing from the study must be informed by the investigator about modified follow-up options (eg, telephone contact, a contact with a relative or treating physician, or information from medical records).
- At the time of withdrawal from the study, if possible, an IPD Visit should be conducted, as shown in the SoA. See the SoA for data to be collected at the time of study withdrawal and follow-up and for any further evaluations that need to be completed.
 - The participant will discontinue the study intervention and be withdrawn from the study at that time.
- If the participant withdraws consent for disclosure of future information, the sponsor may retain and continue to use any data collected before such a withdrawal of consent.
- If a participant withdraws from the study, it should be confirmed if he/she still agrees for existing samples to be used in line with the original consent. If he/she requests withdrawal of consent for use of samples, destruction of any samples taken and not tested should be carried out in line with what was stated in the informed consent and local regulation. The investigator must document the decision on use of existing samples in the site study records and inform the Global Study Team.

The participants will return the study supplied equipment.

7.3 Lost to Follow-up

A participant will be considered lost to follow-up if he/she repeatedly fails to return for scheduled visits and is unable to be contacted by the study site.

The following actions must be taken if a participant fails to return to the clinic for a required

study visit:

- The site must attempt to contact the participant and reschedule the missed visit as soon as possible and counsel the participant on the importance of maintaining the assigned visit schedule and ascertain whether or not the participant wishes to and/or should continue in the study.
- Before a participant is deemed lost to follow-up, the investigator or designee must make
 every effort to regain contact with the participant (where possible, 3 telephone calls and,
 if necessary, a certified letter to the participant's last known mailing address or local
 equivalent methods). These contact attempts should be documented in the participant's
 medical record.
- Should the participant continue to be unreachable, he/she will be considered to have withdrawn from the study.

Discontinuation of specific sites or of the study as a whole are handled as part of Appendix A.

8 STUDY ASSESSMENTS AND PROCEDURES

- Study procedures and their timing are summarised in the SoA. Protocol waivers or exemptions are not allowed.
- Immediate safety concerns should be discussed with the sponsor immediately upon occurrence or awareness to determine if the participant should continue or discontinue study intervention.
- Adherence to the study design requirements, including those specified in the SoA, is essential and required for study conduct.
- All screening evaluations must be completed and reviewed to confirm that potential
 participants meet all eligibility criteria. The investigator will maintain a screening log to
 record details of all participants screened and to confirm eligibility or record reasons for
 screening failure, as applicable.
- Procedures conducted as part of the participant's routine clinical management (eg, blood count) and obtained before signing of the ICF may be utilised for screening or baseline purposes provided the procedures met the protocol-specified criteria and were performed within the time frame defined in the SoA.
- Repeat or unscheduled samples may be taken for safety reasons or for technical issues with the samples.

8.1 Efficacy Assessments

8.1.1 Assessment of OCS Dose

All participants who meet eligibility criteria and enter the study will receive open-label

tezepelumab during the induction phase (Week 0 to Week 4). During this phase, participants should remain stable on their baseline (Week 0) OCS dose.

During the OCS reduction and maintenance phase, participants will reduce their OCS dose until the participant discontinues OCS or reaches the lowest OCS dose possible. OCS dose reduction may be slowed down in case of a first test result indicating complete AI, an elevated ACQ-6 score, or a first asthma exacerbation. OCS dose reduction will be stopped for the duration of the trial in case of a second test result confirming complete AI or a second asthma exacerbation (details provided in Section 8.1.2, Appendix M, and the schedule provided in Table 7).

No further reductions will be made to OCS dose from Week 48 onwards.

In case of exacerbations, participants will be managed as per details provided in Section 6.5.1.1. Additionally, in case the participant experiences asthma deterioration or an exacerbation, increase in the maintenance OCS daily dose is permitted per investigator discretion. Once the participant recovers from the first asthma exacerbation, further OCS dose reductions will be allowed at a slower pace during the reduction and maintenance phase as described in Table 8. No reductions are allowed after a second exacerbation.

All OCS dose changes, including temporary or permanent interruption of OCS reduction, will be documented in the source documentation and recorded in the appropriate eCRF form, along with reason for change.

8.1.2 OCS Dose Titration

At screening visit, participants will continue with or be switched to prednisone/prednisolone. For participants not previously receiving prednisone/prednisolone as OCS, the conversion table shown in Appendix D will be used to calculate the equivalent prednisone/prednisolone dose for dose titration.

The OCS dose titration in the reduction phase will be followed as per Table 7 depending on the initial OCS dose and HPA axis evaluation. Note: For participants who must reduce OCS dose more frequently than Q4W or if the scheduled dose reduction does not coincide with a clinic visit (see reduction scheme in Table 7), OCS dose reduction may occur remotely (eg, by telephone) instead of a clinic visit.

If Table 7 instructs to reduce dose by 5 mg increments, but the initial OCS dose is < 5 mg to the nearest dosing level, the 1st reduction would be smaller, rounding down to the nearest 5 mg, then continue on with 5 mg Q2W reductions (examples below):

- eg, $12.5 \rightarrow 10 \text{ mg} \rightarrow \text{etc.}$
- eg, $23 \rightarrow 20 \rightarrow 15 \rightarrow 10 \text{ mg} \rightarrow \text{etc.}$

• eg, $19 \rightarrow 15 \rightarrow 10 \text{ mg} \rightarrow \text{etc.}$

If Table 7 instructs to reduce the initial dose by 2.5 mg increments, but the initial dose is < 2.5mg to the next dosing level, the 1st reduction would be smaller, rounding down to the nearest 2.5 mg, then continue on with 2.5 Q4W reductions (examples below):

- eg, $8 \rightarrow 7.5 \rightarrow 5 \rightarrow \text{etc.}$
- eg, $6.25 \rightarrow 5 \rightarrow$ etc.

Investigators may also choose to slow the down-titration to 1 mg Q4W once the participant reaches an OCS dose of 5 mg/day based on participant symptoms.

For all participants, HPA axis integrity will be evaluated after 4 weeks on 5 mg/day and prior to tapering down the OCS dose (for participants with baseline OCS doses equal to 5 mg/day, this will be assessed 4 weeks after the first dose of tezepelumab administration and before initiation of the OCS reduction and maintenance phase). See Section 8.2.1 for details.

Table 7

OCS Dose Titration Schedule During the OCS Reduction and Maintenance Phase

Initial OCS	OCS down-titration to reach		an OCS dose of:		
dose/day					
	20 mg	10 mg	7.5 mg	5 mg	0 mg
> 20 mg	Reduction of 5 mg	Reduction of	2.5 mg of the	2.5 mg of the	No AI: reductions of 2.5 mg of the daily dose Q4W until reaching dose
	of the daily dose	5 mg of the	daily dose Q2W	daily dose Q4W	of 0 mg/day
	weekly until	daily dose Q2W	until reaching	until reaching	Partial AI: reductions of 1 mg of the daily dose Q4W and repeat test
	reaching dose of	until reaching	dose of	dose of	2 months later ^a
	20 mg/day	dose of	7.5 mg/day	5 mg/day	Complete AI: No OCS dose reduction and repeat test 3 months later ^b
		10 mg/day			
$> 10 \text{ mg to} \le 20 \text{ mg}$		Reduction of	2.5 mg of the	2.5 mg of the	No AI: reductions of 2.5 mg of the daily dose Q4W until reaching dose
		5 mg of the	daily dose Q2W	daily dose Q4W	of 0 mg/day
		daily dose Q2W	until reaching	until reaching	Partial AI: reductions of 1 mg of the daily dose Q4W and repeat test 2
		until reaching	dose of	dose of	months latera
		dose of	7.5 mg/day	5 mg/day	Complete AI: No OCS dose reduction and repeat test 3 months later ^b
		10 mg/day			
> 7.5 mg to			2.5 mg of the	2.5 mg of the	No AI: reductions of 2.5 mg of the daily dose Q4W until reaching dose
≤ 10 mg			daily dose Q2W	daily dose Q4W	of 0 mg/day
			until reaching	until reaching	Partial AI: reductions of 1 mg of the daily dose Q4W and repeat test
			dose of	dose of	2 months later ^a
			7.5 mg/day	5 mg/day	Complete AI: No OCS dose reduction and repeat test 3 months later ^b
$> 5 \text{ mg to} \le 7.5 \text{ mg}$				2.5 mg of the	No AI: reductions of 2.5 mg of the daily dose Q4W until reaching dose
				daily dose Q4W	of 0 mg/day
				until reaching	Partial AI: reductions of 1 mg of the daily dose Q4W and repeat test 2
				dose of	months later ^a
				5 mg/day	Complete AI: No OCS dose reduction and repeat test 3 months later ^b
5 mg					No AI: reductions of 2.5 mg of the daily dose Q4W until reaching dose
					of 0 mg/day
					Partial AI: reductions of 1 mg of the daily dose Q4W and repeat test
					2 months later ^a
					Complete AI: No OCS dose reduction and repeat test 3 months later ^b
a Partial AI cortisol test	ing confirmed with A(CTH stimulation tes	ting or the alternativ	ve method described	Partial AI contismed with ACTH stimulation testing or the alternative method described in Amendix M. After renetition of the test 2 months later the decision to

^a Partial AI cortisol testing confirmed with ACTH stimulation testing or the alternative method described in Appendix M. After repetition of the test 2 months later, the decision to further reduce OCS dose will be based on the morning cortisol test results. If test results are normal, the OCS dose may be reduced directly to 0 mg/day (if participant is receiving

^{≤3} mg); the participant will continue receiving 1 mg Q4W if still at risk. If complete AI is indicated, OCS dose will not be modified.
b If morning cortisol test results again indicate complete AI at 3 months, the OCS dose will not be modified as this is the final attempt. If morning cortisol test results indicate risk AI, then reductions will be 1 mg Q4W and, if normal, then reductions will be 2.5 mg Q4W.

Rescue OCS Down-titration After Recovery From the First Event of an Asthma Exacerbation or Deterioration Table 8

Initial OCS dose/day	Rescue OCS down-titration af	ter recovery from an asthma exacerbation	after recovery from an asthma exacerbation or deterioration to reach an OCS dose of:
	10 mg	5 mg	0 mg
> 20 mg	Reduction of 5 mg of the daily dose Q4W until reaching a dose of 10 mg/day	Reduction of 2.5 mg of the daily dose Q4W until reaching a dose of 5 mg/day	No AI: Reduction of 2.5 mg of the daily dose Q4W Partial AI: 1 mg/day of the daily dose Q4W and repeat test 2 months later ^a Complete AI: No OCS dose reduction and repeat test 3 months later ^b
> 10 mg to ≤ 20 mg	Reduction of 5 mg of the daily dose Q4W until reaching a dose of 10 mg/day	Reduction of 2.5 mg of the daily dose Q4W until reaching a dose of 5 mg/day	No AI: Reduction of 2.5 mg of the daily dose Q4W Partial AI: 1 mg/day of the daily dose Q4W and repeat test 2 months later ^a Complete AI: No OCS dose reduction and repeat test 3 months later ^b
> 5 mg to ≤ 10 mg		Reduction of 2.5 mg of the daily dose Q4W until reaching a dose of 5 mg/day	No AI: Reduction of 2.5 mg of the daily dose Q4W Partial AI: 1 mg/day of the daily dose Q4W and repeat test 2 months later ^a Complete AI: No OCS dose reduction and repeat test 3 months later ^b
S mg			No AI: Reduction of 2.5 mg of the daily dose Q4W Partial AI: 1 mg/day of the daily dose Q4W and repeat test 2 months later ^a Complete AI: No OCS dose reduction and repeat test 3 months later ^b

^a Partial AI cortisol testing confirmed with ACTH stimulation testing or the alternative method described in Appendix M. After repetition of the test 2 months later, the decision to further reduce OCS dose will be based on the morning cortisol test results. If test results are normal the OCS dose may be reduced directly to 0 mg/day (if participant was receiving

 ^{≤ 3} mg); the participant will continue receiving 1 mg Q4W if still at risk.
 b If morning cortisol test results again indicate complete AI at 3 months, the OCS dose will not be modified as this is the last attempt. If morning cortisol test results indicate risk AI, then reductions will be 1 mg Q4W and, if normal, then reductions will be 2.5 mg Q4W.

For prednisone/prednisolone doses below 5 mg, if the exact dose strength is not available in the country, the daily dose to be administered could be achieved by dosing every other day. Daily dose will be the average of 2 days. See Appendix E for help dosing < 5 mg in relation to tablet strength.

8.1.2.1 Asthma Worsening or Exacerbation Preventing OCS Down-titration The OCS dose titration will be interrupted in case of one of the following circumstances related to the asthma condition:

- Asthma deterioration will be assessed by the investigators when there is an increase in ACQ-6 scores of ≥ 0.5 from the value at Visit 2. If the ACQ-6 score at Visit 2 is missing, the 1st score recorded post-Visit 2 and pre-OCS reduction may be used as baseline value for the 0.5-point increase (however, it will not be used to impute the baseline for ACQ-6 analysis). At each visit, in addition to the participant's asthma symptoms, investigators will use the participant's weekly ACQ-6 scores and will further reduce the OCS dose unless asthma control is lost or AI prevents further dose reduction.
- In case of an asthma exacerbation that requires treatment with a temporary bolus/burst of systemic corticosteroids (or a temporary increase in stable OCS background dose) for at least 3 consecutive days², in-patient hospitalisation, or ER admission, the OCS dose titration will be interrupted, and appropriate treatment will be administered as described in Section 6.5.1.1.
- After recovery from the first asthma deterioration or exacerbation, participants will be
 offered to continue OCS tapering down at a slower speed (ie, Q4W). If the first asthma
 deterioration or exacerbation occurs between Week 48 and Week 52, no further
 down-titration will be allowed.

² A single depo-injectable dose of corticosteroids will be considered equivalent to a 3-day bolus/burst of systemic corticosteroids.

In the case of a second event of asthma deterioration or exacerbation, the OCS reduction will be stopped, and the participant will continue on the same OCS dose or will return to a one-step higher dose level (or more as considered necessary by the investigator).

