because of loss of asthma control and/or evidence of AI, as measured by cortisol levels (morning cortisol level or adrenocorticotropic hormone [ACTH] stimulation test).

Table A Oral Corticosteroid Titration Schema Until Reaching 5 mg/day

Baseline OCS dose	OCS down-titration schema until reaching 5 mg/day (without worsening of asthma)
> 20 mg/day	Reductions of 5 mg of the daily dose every 1 week until reaching a dose of 20 mg/day; followed by reductions of 5 mg every 2 weeks (Q2W) until a dose of 10 mg/day is reached; followed by reductions of 2.5 mg Q2W until reaching a dose of 7.5 mg/day; and then reductions of 2.5 mg Q4W until reaching a dose of 5 mg/day
> 10 to ≤ 20 mg/day	Reductions of 5 mg of the daily dose Q2W until reaching a dose of 10 mg/day; followed by reductions of 2.5 mg Q2W until reaching a dose of 7.5 mg/day; and then reductions of 2.5 mg Q4W until reaching a dose of 5 mg/day
> 7.5 to ≤ 10 mg/day	Reductions of 2.5 mg of the daily dose Q2W until reaching a dose of 7.5 mg/day followed by reductions of 2.5 mg Q4W until reaching a dose of 5 mg/day
> 5 to ≤ 7.5 mg/day	Reductions of 2.5 mg of the daily dose Q4W until reaching a dose of 5 mg/day

Abbreviations: OCS = oral corticosteroids; Q2W = every two weeks; Q4W = every four weeks.

Once a participant reaches the lowest stable dose, the participant will be considered in maintenance. From Week 48 to Week 52, all participants will remain on their stable daily OCS dose, except if an asthma deterioration or exacerbation occurs. No further down-titration will be allowed from Week 48 onwards.

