- ^e For participants who have reached OCS doses equal to 5 mg/day, hypothalamic-pituitary-adrenal (HPA) axis integrity will be assessed at the end of a 4-week period on 5 mg/day using the 8 to 9 am morning cortisol level. If the morning cortisol level is indeterminate, then an ACTH stimulation or alternative method is required within approximately 1 week. For those participants who had a baseline OCS dose equal to 5 mg/day, HPA axis integrity will be assessed 4 weeks after first dose of tezepelumab administration and before initiation of the OCS reduction and maintenance phase.
- ^f For sites where no tetracosactide is available/registered, an alternative method to identify adrenal insufficiency is provided (see Appendix M).
- g Only events that fall into the following categories are collected in this study: SAEs, DAEs, and AESIs. AEs of special interest in this study fall into the following categories: serious hypersensitivity reactions (see Appendix G), serious infections (including serious opportunistic infections), helminth infections, serious cardiac events, malignancy, Guillain Barre syndrome, and adrenal crisis.
- hAt Visit 2, assessment should be performed before any other study procedures. After Visit 2, any available PROs which have not been completed prior to the site visit, should be completed at the site prior to any other study procedure.
- ⁱ The ACQ-6 will be completed every 1 week at home on the handheld device.
- AQLQ(s)+12, SGRQ, SNOT-22 and PPOCS are to be completed at home as per Schedule of Activities (within a defined window of ± 2 days; this defined window may or may not coincide with the on-site visit).
- k Oral corticosteroid dose reduction is for participants who have not reached the lowest possible stable dose, and who have not lost asthma control. No further OCS dose reduction will be allowed from Week 48 onwards. Note that for participants who must reduce OCS dose more frequently than every 4 weeks or between site visits (see reduction scheme in Table 7), OCS dose reduction may occur remotely (eg, by telephone) instead of a clinic visit.
- Oral corticosteroid dose reduction not allowed at Week 48.
- ^m For participants who prematurely discontinue study drug and do not want to undergo further study assessments, apart from phone call 52 weeks after baseline (see Section 7.1).
 - ⁿ At Visit 2, all assessments should be done before tezepelumab administration to ensure proper calculation of baseline values.

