- 2. **Induction phase From Week 0 to 4:** After confirmation of eligibility criteria, participants will start receiving tezepelumab treatment at Visit 2/Week 0 (baseline) and should remain stable on their baseline OCS dose during this phase.
- 3. Oral corticosteroid reduction and maintenance phase From Week 4 to Week 52: Site visits will occur Q4W. Participants will reduce their dosage of OCS according to the schema defined in Table 7 for each baseline OCS dose until they reach the lowest stable OCS dose or until Week 48. The first OCS dose reduction may occur at Visit 3. OCS dose reduction may occur remotely if the scheduled dose reduction does not coincide with a site visit.

Participants will be considered as having reached the lowest stable dose when they have discontinued OCS or no further OCS reduction is possible because of loss of asthma control and/or evidence of AI (as confirmed by morning cortisol test or adrenocorticotropic hormone [ACTH] stimulation test).

Once they reach the lowest stable dose, participants will be considered in maintenance. From Week 48 to Week 52, all participants will remain on their stable daily OCS dose, except if an asthma deterioration or exacerbation occurs. No further down-titration will be allowed from Week 48 onwards.

HPA axis integrity will be evaluated for all participants who have been on 5 mg/day OCS for 4 weeks and prior to any further tapering down the OCS dose (for participants with baseline OCS doses equal to 5 mg/day, this will be assessed 4 weeks after the first dose of tezepelumab administration and before initiation of the OCS reduction and maintenance phase). A screening method with morning serum cortisol (see Section 8.2.1.1) will be done (8 to 9 am morning cortisol level), to evaluate whether the participant has normal cortisol levels or complete AI. Cortisol levels from the morning cortisol test that will be below normal range and above the complete AI range will be considered 'indeterminate' and will require additional testing (ACTH stimulation test or alternative method, as described in Appendix M).

Depending on the morning cortisol level results, the participant will continue per the following guidance:

- Cortisol levels within normal range (Table 9):
 - Participant exhibits absence of signs and/or symptoms of AI: continue OCS down-titration by 2.5 mg Q4W
 - Participant exhibits signs and/or symptoms of AI: continue OCS down-titration at a slower pace (1 mg Q4W)

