- 3. Oral corticosteroid reduction and maintenance phase From Week 4 to Week 52: Site visits occur Q4W. Participants reduce their dosage of OCS according to the schema defined in the CSP Table 7 for each baseline OCS dose until they reach the lowest stable OCS dose or until Week 48. The first OCS dose reduction may occur at Visit 3. OCS dose reduction may occur remotely if the scheduled dose reduction does not coincide with a site visit.

Participants are considered as having reached the lowest stable dose when they have discontinued OCS or no further OCS reduction is possible because of loss of asthma control and/or evidence of AI (as confirmed by morning cortisol test or adrenocorticotropic hormone [ACTH] stimulation test).

Once they reach the lowest stable dose, participants are considered in maintenance period. From Week 48 to Week 52, all participants remain on their stable daily OCS dose, except if an asthma deterioration or exacerbation occurs. No further down-titration are allowed from Week 48 onwards.

The evaluation of the HPA axis integrity starts for all participants who have been on 5 mg/day OCS. A screening method with morning serum cortisol is done to evaluate whether the participant has normal cortisol levels or complete AI. Cortisol levels from the morning cortisol test below normal range and above the complete AI range are considered 'indeterminate' and will require additional testing (ACTH stimulation test or alternative method). Further details are provided in the CSP Section 8.2.1 and CSP Appendix M).

At each visit, in addition to the participant's asthma symptoms, investigators use the participant's weekly ACQ-6 scores (completed by the participant at home by means of a handheld electronic participant-reported outcome device [ePRO]), and further reduce the OCS dose unless asthma control is lost (deterioration or exacerbation as described below) or AI prevents further dose reduction.

[figure not shown]
Asthma deterioration is defined by an increase of ACQ-6 score \geq 0.5 from baseline. Asthma exacerbation is defined by worsening of asthma symptoms that leads to:

- A temporary bolus/burst of systemic corticosteroids (or a temporary increase in stable OCS background dose) for at least 3 consecutive days to treat symptoms of asthma worsening; a single depo-injectable dose of corticosteroids will be considered equivalent to a 3-day bolus/burst of systemic corticosteroids.

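### For baseline OCS doses above 25 mg/day that are not multiples of 5, the Section 8.1.2 rounding rule gives two-weekly cuts where Table 7 requires weekly cuts (minor)

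*Protocol*

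**What the plan says.** Table A in the Protocol Synopsis gives the taper for baselines above 20 mg/day: "Reductions of 5 mg of the daily dose every 1 week until reaching a dose of 20 mg/day", then 5 mg every 2 weeks to 10 mg/day, 2.5 mg every 2 weeks to 7.5 mg/day, and 2.5 mg every 4 weeks to 5 mg/day. The > 20 mg row of Table 7 has the same weekly interval down to 20 mg/day.

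Section 8.1.2 adds a rule for starting doses that do not sit on a 5 mg level. Its trigger is "If Table 7 instructs to reduce dose by 5 mg increments", and its instruction is that "the 1st reduction would be smaller, rounding down to the nearest 5 mg, then continue on with 5 mg Q2W reductions". It makes no exception for doses above 20 mg/day. Three examples follow, starting from 12.5, 23 and 19 mg.

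The same section also states "The OCS dose titration in the reduction phase will be followed as per Table 7". Protocol Section 4.1 ("Participants will reduce their dosage of OCS according to the schema defined in Table 7 for each baseline OCS dose"), Protocol Section 8.1.1, footnote k of the Schedule of Activities and SAP Section 1.2 point to the same table.

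**The concern.** The trigger covers the weekly part of the > 20 mg row, because that part also uses 5 mg steps. A participant starting at 38 mg/day is therefore told to cut weekly by Table 7 and every 2 weeks by the rounding sentence. The sentence is the one written for exactly this kind of dose, so it is where a site would look.

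Nothing else in the protocol supports a two-weekly interval above 20 mg/day. The slowing provisions in Section 8.1.1 need a first complete adrenal insufficiency result, a raised ACQ-6 score or a first exacerbation. The elective 1 mg taper starts only at 5 mg/day. The rescue taper in Table 8 is every 4 weeks.

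What is at stake is the timing of the taper, the date of the adrenal test at 5 mg/day, steroid exposure and, at the margin, Week 28 discontinuation status, which is a primary endpoint. Section 4.2 makes the appropriateness of a faster taper part of the study question, and Section 8 allows no protocol waivers, so two intervals for the same step also leave it unclear which taper is compliant.

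**Working it through.** **Which doses are affected**

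The first cut rounds down to a multiple of 5. The 19 → 15 mg example shows that levels are multiples of 5, not only the Table 7 column doses.

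- The protocol's own examples (12.5 → 10; 23 → 20 → 15 → 10; 19 → 15 → 10) come out the same under both rules. Each is at 20 mg or less after the first cut, where Table 7 is itself two-weekly, so none of them settles the conflict.
- Comparing the two rules for every baseline from 10.5 to 40 mg in 0.5 mg steps, they agree up to 25 mg and at every multiple of 5. They differ at every other dose above 25 and below 40 mg.

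Such baselines are eligible. Section 5.1 allows up to 40 mg/day and accepts averaged non-daily regimens. Conversion by Appendix D can also produce them: methylprednisolone 30 mg gives 30 × 10/8 = 37.5 mg, and dexamethasone 4 mg gives 4 × 10/1.5 = 26.7 mg.

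**Assumptions for the timing**

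The first cut is at Week 4, the taper is uninterrupted, and each interval is the wait before the next cut. The participant spends 4 weeks on 5 mg, has a normal adrenal result, and then takes two 2.5 mg steps 4 weeks apart. An ACTH test after an indeterminate cortisol may add about 1 week (Section 4.1), which moves each 0 mg date by 1 week.

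**Worked path, 38 mg, no test delay**

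| Dose (mg/day) | 35 | 30 | 25 | 20 | 15 | 10 | 7.5 | 5 | 2.5 | 0 |
|---|---|---|---|---|---|---|---|---|---|---|
| Table 7, week | 4 | 5 | 6 | 7 | 9 | 11 | 13 | 17 | 21 | 25 |
| Sentence, then Table 7 from 10 mg, week | 4 | 6 | 8 | 10 | 12 | 14 | 16 | 20 | 24 | 28 |

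**All affected baselines, no test delay (Table 7 vs sentence)**

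| Baseline (mg/day) | 20 mg reached | 5 mg reached | 0 mg reached | Delay |
|---|---|---|---|---|
| > 25 to < 30 | Week 5 vs 6 | Week 15 vs 16 | Week 23 vs 24 | 1 week |
| > 30 to < 35 | Week 6 vs 8 | Week 16 vs 18 | Week 24 vs 26 | 2 weeks |
| > 35 to < 40 | Week 7 vs 10 | Week 17 vs 20 | Week 25 vs 28 | 3 weeks |

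**Extra prednisone per participant**

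Each level between the first cut and 20 mg is held for one extra week. Dividing by 28 × 7 = 196 days gives the effect on the SAP's 28-week mean daily systemic corticosteroid exposure, with no test delay.

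- > 25 to < 30: 25 × 7 = 175 mg; 175/196 = 0.9 mg/day
- > 30 to < 35: (30 + 25) × 7 = 385 mg; 385/196 = 2.0 mg/day
- > 35 to < 40: (35 + 30 + 25) × 7 = 630 mg; 630/196 = 3.2 mg/day

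**Week 28 discontinuation**

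Table 13 requires a dose unchanged for at least 2 weeks but does not say whether those weeks must be over by Week 28.

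- If they must, 0 mg is needed by Week 28 − 2 = Week 26. Above 35 mg, status changes with or without the test delay (Week 25 or 26 vs 28 or 29). From > 30 to < 35 mg, it changes only with the delay (25 vs 27). Below 30 mg it does not change (23 or 24 vs 24 or 25).
- If reaching 0 mg by Week 28 is enough, only baselines above 35 mg with the test delay change (26 vs 29).

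In every case 5 mg is reached by Week 20 and 0 mg by Week 29, so the ≤ 5 mg endpoint at Week 28 and both endpoints at Week 52 keep the same value.

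**The case against.** The strongest reply is that the documents already answer the question. Section 8.1.2 opens by making Table 7 the schedule, several other sections and the SAP refer to it, and Table A repeats its intervals. The rounding sentence mainly sets the size of an odd first step, and its examples are all correct. To go wrong, a site must let a trailing clause override an explicit weekly entry.

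The consequence is also conditional. It needs an unusual baseline, a site that follows the sentence, and a smooth taper. Most of the Week 28 effect further needs a stability rule that neither document states. The primary lock includes data after Week 28 (SAP Sections 3.1 and 3.3.1.1), so stability could be confirmed later. The error makes the taper slower, which is the cautious direction. Practical prescribing would also avoid many of these doses: 26.7 mg is an unlikely prescription, and methylprednisolone in multiples of 4 mg converts to multiples of 5 mg.

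Most of this stands, and it is why the point is minor. It does not remove the contradiction. The sentence is a specific dosing instruction for off-level doses, and for eligible doses above 25 mg/day the interval it gives is wrong.

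**Conclusion.** The concern holds and is minor. The rounding sentence conflicts with Table A and Table 7 for baselines above 25 and below 40 mg/day that are not multiples of 5. That Table 7 is intended is an inference, but a well-supported one.

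A site following the sentence literally would taper up to 3 weeks late, with up to 630 mg more prednisone per participant. Under the assumptions above, only discontinuation at Week 28 can change among the primary endpoints, mainly for baselines above 35 mg/day and depending on how the stability rule is read. The documents do not say how many participants have such baselines; the number is probably very small, and no effect on the trial's conclusions is shown. Confidence in the conflict is high; the Week 28 effect rests on the stated assumptions.

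**What to change.** In Section 8.1.2, replace the closing instruction of the rounding sentence with one that continues at the Table 7 step and interval for the current dose: 5 mg weekly until 20 mg/day, then 5 mg every 2 weeks until 10 mg/day. Add an example that passes through the weekly segment, such as 38 → 35 → 30 → 25 → 20 mg weekly, then 15 → 10 mg every 2 weeks.

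The cost is one sentence and one example in a protocol clarification, plus a note to sites. Sample size, endpoints and analysis do not change.
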